8.0 STATISTICAL AND ANALYTICAL PLAN

This section outlines the statistical analysis strategy and procedures for the study. If, after the study has begun, but prior to any unblinding, changes are made to primary and/or secondary hypotheses, or the statistical methods related to those hypotheses, then the protocol will be amended (consistent with ICH Guideline E-9). Changes to exploratory or other non-confirmatory analyses made after the protocol has been finalized, along with an explanation as to when and why they occurred, will be listed in the Clinical Study Report (CSR) for the study. Post hoc exploratory analyses will be clearly identified in the CSR. No separate Statistical Analysis Plan (SAP) will be issued for this study.

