8.3.2 Safety Endpoints

An initial description of safety measures is provided in [Section 7.7.2](#).

The analysis of safety results will follow a tiered approach. The tiers differ with respect to the analyses that will be performed. Safety parameters or adverse experiences of special interest that are identified *a priori* constitute “Tier 1” safety endpoints that will be subject to inferential testing for statistical significance with p-values and 95% confidence intervals provided for between-group comparisons. Other safety parameters will be considered Tier 2 or Tier 3. Tier 2 parameters (requires that at least 4 patients in any treatment group exhibit the event) will be assessed via point estimates with 95% confidence intervals provided for between-group comparisons; only point estimates by treatment group are provided for Tier 3 safety parameters.

The following four categories are Tier 1 events[†]:

- Hepatic safety: Elevated AST or ALT lab value that is ≥ 3 x the upper limit of normal (ULN) and an elevated total bilirubin lab value that is ≥ 2 x ULN and, at the same time, an alkaline phosphatase lab value that < 2 ULN, as determined by way of protocol-specified laboratory testing or unscheduled laboratory testing;
- CNS and visual safety: Treatment-emergent adverse events (TEAEs) related to visual and CNS disturbances. See [Section 8.5.2](#) for a list of terms
- Dermatologic reactions: TEAEs including rash and photosensitivity rash;
- Adrenal steroidogenesis: TEAEs indicating adrenal insufficiency or temporally associated TEAEs of hypotension.

[†] The team has listed specific terms, see section 8.5.2, that they believe fall under these broader categories, however these categories may include additional related terms when full data reporting for the study is complete.

The following are Tier 2 events based on specific AE categories: (1) at least one adverse experience; (2) drug related adverse experience; (3) serious adverse experience; (4) serious and drug related adverse experience; (5) discontinued study therapy due to an adverse experience.

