8.5.2 Statistical Methods for Safety Analyses

Safety and tolerability will be assessed by clinical review of all relevant parameters including adverse experiences (AEs), laboratory tests, vital signs, and ECG measurements.

The analysis of safety results will follow a tiered approach ([Table 14](#)). The tiers differ with respect to the analyses that will be performed. Safety parameters or adverse experiences of special interest that are identified *a priori* constitute "Tier 1" safety endpoints that will be subject to inferential testing for statistical significance with p-values and 95% confidence intervals provided for between-group

comparisons. Other safety parameters will be considered Tier 2 or Tier 3. Tier 2 parameters will be assessed via point estimates with 95% confidence intervals provided for between-group comparisons; only point estimates by treatment group are provided for Tier 3 safety parameters.

Adverse experiences (specific terms as well as system organ class terms) and predefined limits of change in laboratory, vital signs, and ECG parameters that are not pre-specified as Tier-1 endpoints prior to database lock will be classified as belonging to "Tier 2" or "Tier 3", based on the number of events observed. Membership in Tier 2 requires that at least 4 subjects in any treatment group exhibit the event; all other adverse experiences and predefined limits of change will belong to Tier 3.

The threshold of at least 4 events was chosen because the 95% confidence interval for the between-group difference in percent incidence will always include zero when treatment groups of equal size each have less than 4 events and thus would add little to the interpretation of potentially meaningful differences. Because many 95% confidence intervals may be provided without adjustment for multiplicity, the confidence intervals should be regarded as a helpful descriptive measure to be used in review, not a formal method for assessing the statistical significance of the between-group differences in adverse experiences and predefined limits of change.

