Tier 2 analysis of treatment difference and 95% CI will be provided for the following events based on specific AE categories: (1) at least one adverse experience; (2) drug related adverse experience; (3) serious adverse experience; (4) serious and drug related adverse experience; (5) discontinued study therapy due to an adverse experience. Other AE categories such as SOCs (System Organ Class) or PDLC (Pre-Defined Limit of Change) in which there are more than 4 events in both groups, Tier 2 analysis of treatment difference and 95% CI will also be provided.

Table 14 Analysis Strategy for Safety Parameters

Safety Tier	Safety Endpoint ^a	p-Value	95% CI for Treatment Comparison	Descriptive Statistics
Tier 1	
 •Hepatic Safety •CNS and visual safety •Dermatologic reactions •Adrenal steroidogenesis 	X	X	X
Tier 2	Proportion of subjects: (1) with at least one AE (2) with a drug related AE (3) with a serious AE (4) with serious and drug related AE (5) discontinued study therapy due to an adverse experience Specific AEs, SOCs, or PDLCs (incidence ≥4 of subjects in one of the treatment groups)		X	X
Tier 3	Specific AEs, SOCs or PDLCs (incidence <4 of subjects in all of the treatment groups) Change from baseline in laboratory measurements			X

^a Adverse Experience references refer to both Clinical and Laboratory AEs.

Note: SOC=System Organ Class; PDLC=Pre-Defined Limit of Change; a listing of subjects and their values falling outside the PDLC will also be provided; X = results will be provided; AE = Adverse Experience

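### Section 8.5.2 sets a different, stricter count threshold for Tier 2 confidence intervals in SOC and PDLC categories than Sections 8.3.2 and 8.5.2 and Table 14 set elsewhere

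*Combined protocol and SAP*

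**What the plan says.** Three places give one rule for Tier 2, the tier that reports a between-arm difference with a 95% CI:

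- Section 8.3.2: Tier 2 "requires that at least 4 patients in any treatment group exhibit the event".
- Section 8.5.2, early paragraph: "Membership in Tier 2 requires that at least 4 subjects in any treatment group exhibit the event". Everything else goes to Tier 3. The reason given for the cut-off is that the interval "will always include zero when treatment groups of equal size each have less than 4 events".
- Table 14: specific AEs, SOCs and PDLCs are Tier 2 with "incidence ≥4 of subjects in one of the treatment groups", and Tier 3 when the count is below 4 "of subjects in all of the treatment groups".

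The sentence directly before Table 14 covers the same SOC and PDLC categories and states a different condition: those "in which there are more than 4 events in both groups, Tier 2 analysis of treatment difference and 95% CI will also be provided".

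Section 8.0 adds: "No separate Statistical Analysis Plan (SAP) will be issued for this study".

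**The concern.** The sentence before Table 14 changes the cut-off (more than 4, so 5 or more, instead of 4 or more) and the quantifier (both arms instead of any arm). It also says events where the tier rule says subjects.

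The quantifier matters most. The plan's reason for a threshold of 4 is that smaller counts cannot produce an interval excluding zero. A both-arms condition does not serve that purpose. It removes categories in which one arm has few or no events, and those are the ones that can show an imbalance.

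Since no separate SAP will follow, this text is the programming specification. Two competent programmers could produce different safety tables, and the choice between two written rules might be made once counts by arm are known.

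**Working it through.** **Inputs.** Arm size is 300 (also 285 and 270), from Section 8.7.3. The interval is the 95% Miettinen-Nurminen CI, from Section 7.7.2.1 and Appendix 7, unstratified. Rule A is four or more subjects in at least one arm (8.3.2, 8.5.2, Table 14). Rule B is more than 4 in each arm (the sentence before Table 14). Each subject is counted once. Event counts and incidences are assumptions, because the documents give none for SOC or PDLC categories.

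**Step 1: reproduce the plan's reason for 4.** The interval excludes zero when the Appendix 7 statistic at a zero difference exceeds 1.96. With arms of size n, counts a and b, and pooled p = (a + b)/(2n):

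z = [(a - b)/n] / sqrt{ p(1 - p) × (2/n) × 2n/(2n - 1) }

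At n = 300:

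- 3 v 0: p = 3/600 = 0.005, z = 0.0100/0.00576 = 1.74. CI -0.27 to 2.90 points, which includes zero.
- 4 v 0: p = 4/600 = 0.00667, z = 0.01333/0.00665 = 2.01. CI 0.06 to 3.38, which excludes zero.

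All 16 pairs with both arms below 4 include zero at 300, 285 and 270 per arm. The stated reason is correct, and Rule A starts exactly where an interval can first exclude zero.

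**Step 2: apply both rules to hypothetical counts (300 per arm).**

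| Counts | 95% CI (points) | Rule A | Rule B |
|---|---|---|---|
| 4 v 0 | 0.06 to 3.38 | CI | none |
| 12 v 4 | 0.10 to 5.69 | CI | none |
| 30 v 4 | 5.28 to 12.73 | CI | none |
| 0 v 15 | -8.09 to -3.05 | CI | none |
| 5 v 5 | -2.38 to 2.38 | CI | CI |

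With 0, 1, 2, 3 or 4 in the smaller arm, the interval first excludes zero at 4, 7, 9, 10 or 12 in the other arm (10 v 3 is borderline). None of these meets Rule B.

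**Step 3: try the combined-count reading.** If both groups means the two arms added together, 4 v 0 (total 4) gets no interval although Table 14 makes it Tier 2. Conversely, 3 v 3 (total 6) gets one although Table 14 makes it Tier 3. The conflict remains.

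**Step 4: how often the rules disagree.** Let X1 and X2 be independent Binomial(300, p1) and Binomial(300, p2). Any pair meeting Rule B also meets Rule A, so

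P(A but not B) = {1 - P(X1 ≤ 3)P(X2 ≤ 3)} - P(X1 ≥ 5)P(X2 ≥ 5)

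| Assumed true rates | P(A) | P(B) | A but not B |
|---|---|---|---|
| 1% v 1% | 0.581 | 0.034 | 0.547 |
| 2% v 2% | 0.978 | 0.515 | 0.463 |
| 3% v 3% | 1.000 | 0.898 | 0.102 |
| 4% v 4% | 1.000 | 0.986 | 0.0135 |
| 5% v 5% | 1.000 | 0.999 | 0.0014 |
| 3% v 1% | 0.987 | 0.174 | 0.813 |
| 5% v 1% | 1.000 | 0.184 | 0.816 |

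**Step 5: how often an interval that excludes zero would be withheld.** The same enumeration, restricted to outcomes whose interval excludes zero:

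| Assumed true rates | CI excludes zero | Share of those failing Rule B |
|---|---|---|
| 3% v 1% | 42% | 98% |
| 5% v 1% | 86% | 88% |
| 5% v 2% | 53% | 48% |
| 8% v 3% | 79% | 7% |
| 10% v 5% | 66% | 0.1% |

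The effect is confined to categories that are uncommon in at least one arm.

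**The case against.** The best reply is that the sentence promises an additional analysis and never says that only those categories qualify. Every category it covers is already Tier 2 under Table 14, so it can be read as a redundant sufficient condition that takes nothing away. On that reading 0 v 15 is still owed an interval under the other three statements, and Table 14, which names SOCs and PDLCs, follows immediately.

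That reading is logically open, and the rule stated three times may well prevail in practice. But it leaves the sentence with no function, and nothing tells the programmer to ignore its threshold. Steps 2, 4 and 5 therefore show what happens if it is applied as a filter, not what must happen.

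Other points narrow the impact and are accepted:

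- Section 8.5.2 itself uses events and subjects loosely, so the change of unit carries little weight. Counting repeat events would let more categories meet Rule B, which makes the disagreement figures upper bounds.
- With equal true rates, the interval excludes zero in only about 5% of trials, so most intervals lost there are uninformative.
- The share withheld depends heavily on assumed incidence, and SOCs pool many terms, so many will be too common to be affected.
- Counts by arm are still reported, and the note to Table 14 promises a listing of subjects outside a PDLC. A reader could compute the interval.
- Section 8.0 allows changes to non-confirmatory analyses to be documented in the study report.

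None of these removes the presence of two thresholds for the same categories.

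**Conclusion.** The concern holds. The sentence before Table 14 is inconsistent with Section 8.3.2, with the earlier rule in Section 8.5.2 and its stated reason, and with Table 14. Neither the per-arm nor the combined-count reading reproduces the Table 14 threshold.

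The practical impact is low. It reaches only descriptive, unadjusted intervals for AE categories such as SOCs and PDLCs outside Tier 1 and outside the five named Tier 2 summaries. No hypothesis test, alpha level, power figure or efficacy result depends on it.

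Within that scope, the size depends on assumed incidence and on the sentence being used as a filter. Disagreement is substantial at true rates of 1% to 2% in both arms, or where one arm is near 1%. It is negligible at 4% and above in both arms. The wording conflict is certain; the withheld intervals are conditional. It should be corrected because it is cheap to settle now and awkward to settle once the arms are known.

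**What to change.** Before unblinding, replace the sentence with one that carries the existing rule, for example: the Tier 2 difference and 95% CI will also be given for any other AE category, SOC or PDLC that occurs in four or more subjects in either arm. This matches Table 14 and counts subjects throughout.

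The cost is one sentence and, compared with the filter reading, a few more interval rows in the safety tables. No new analysis or data are needed.

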8.5.3 Summaries of Baseline Characteristics, Demographics, and Other Analyses

Demographic and Baseline Characteristics

The comparability of the treatment groups for each relevant characteristic will be assessed by the use of tables and/or graphs. No statistical hypothesis tests will be performed on these characteristics. The number and percentage of subjects screened, randomized, the primary reasons for screening failure, and the primary reason for discontinuation will be displayed. Demographic variables (e.g., age, gender, race, etc.), baseline characteristics, primary and secondary diagnoses, and prior and concomitant therapies will be summarized by treatment either by descriptive statistics or categorical tables.

8.6 Multiplicity

Efficacy

No multiplicity adjustment is necessary as there is only one primary efficacy hypothesis based on a single efficacy endpoint at a single timepoint. Statistical significance in this setting is equivalent to nominal significance and will be based on a one-sided alpha level of 0.025.

If non-inferiority is declared, it can be further concluded that POS is superior to VOR if the lower limit of the CI exceeds zero. Due to the principle of closed testing, no adjustment for multiplicity is required since non-inferiority can always be concluded whenever the data also supports superiority.

Safety

No multiplicity adjustment will be used for the safety analysis.

8.7 Sample Size and Power Calculations

8.7.1 Justification of Non-inferiority Margin for Response Rate

Since both VOR, the current standard of care for IA, and POS are both triazole anti-fungal agents, a non-inferiority design was selected, hypothesizing that POS has at least a similar effect on overall all-cause mortality through Day 42 compared to VOR. In terms of safety, POS may have a better overall profile compared to VOR, notably in terms of hepatic safety, central nervous system and visual side effects. Thus, the intent was to establish POS as an alternative to VOR that was equally efficacious but with improved tolerability.

In terms of assessing non-inferiority, the upper bound of the 95% CI on the difference (POS-VOR) in the all-cause mortality rates will be compared to 10%, the pre-specified non-inferiority margin, as described in Section 8.5.1. A summary of the

statistical power under various assumptions of true clinical mortality rates assuming this margin is presented in Section 8.7.2.

It is noted that the selected margin needs to be relevant in terms of what percentage of the effect VOR above placebo is retained with POS. If the margin for determining the non-inferiority of POS relative to VOR is too large, the possibility exists that POS could be found to be non-inferior to VOR and simultaneously be no better than placebo. Therefore, the size of the non-inferiority margin must be small enough to ensure this does not happen. For example, a NI margin in which more than 50% of the benefit of VOR could be lost would be considered unacceptable. Thus, the rationale for the NI margin of 10% is presented below and based on the preservation of the majority of the effect size (>50%) of VOR compared to placebo under a number of scenarios. Since there are no direct studies of VOR versus placebo in the treatment of IA, the approach consists of linking data from a variety of studies of VOR and the assumed mortality in placebo/untreated patients being treated for acute IA.

8.7.1.1 Summary of Historical Response Data for VOR in IA

The first step in determining a non-inferiority margin is determining that the control treatment had a consistent effect in past studies, i.e., "Historical evidence of sensitivity to drug effects" (HESDE).

A literature search was performed using combinations of search terms such as the following: invasive aspergillosis (IA), VOR, controlled clinical trial. There were no placebo-controlled studies for the treatment of IA, only studies that were active-controlled. Overall, three articles were identified that best described the relevant IA patient population and which contained information about all-cause mortality of VOR versus active control and had sufficient data to assess clinical outcomes on individual patients after a period of observation following completion of antifungal drug treatment [2, 16, 27].

Based on the above data and additional information found in registration documents for VOR [17, 18], we identified 3 clinical trials and used a meta-analysis of the available data to estimate the VOR all-cause mortality rate, which will be used later to determine what percentage of the benefit in efficacy that VOR has over Placebo that would be retained by a 10% NI margin in this study comparing POS to VOR.

The first of the studies included in the meta-analysis below consists of two phase 3 studies 150-307 and 150-602, which enrolled 392 subjects in 1997 through 2000, using identical protocols worldwide (Study 307: Europe, Israel, and Australia; Study 602: US, Canada, Mexico, Brazil, and India), and evaluated VOR versus Amphotericin B (AmB) for the primary treatment of acute IA. Although these are separate studies using identical protocols, the original data analysis plan indicated that these study results were to be combined and as such, the published all-cause mortality rate is combined across both studies [2]. In these combined studies, the all-cause mortality of VOR was 18.8% (27/144, 95% CI 12.7, 26.1) compared to

34.6% (46/133) for patients receiving AmB in the primary treatment of acute IA. The majority of study patients had underlying hematologic malignancies, including bone marrow transplantation. The study also included patients with solid organ transplantation, solid tumors, and AIDS. The patients were mainly treated for definite or probable IA of the lungs. In these 2 studies, VOR was administered with 2 loading doses of 6 mg/kg IV q 12 h followed by 4 mg/kg q 12 h for at least 7 days followed by oral VOR 200 mg BID up to a total of 12 weeks.

In addition to these two combined studies, the meta-analysis was conducted including two additional studies: a study of VOR + Anidulafungin published by Marr et al (2015) [16, 26], and a recent study of ISA versus VOR published by Maertens [27].

The results presented by [26] were based on a prospective, randomized, double-blind clinical trial in allogeneic hematopoietic stem cell transplant (allo-HSCT) recipients and patients with hematological malignancies with proven or probable IA according to the European Organization for Research and Treatment of Cancer (EORTC) and the Mycoses Study Group consensus criteria. Subjects were randomized to receive either VOR monotherapy or VOR in combination with anidulafungin. All subjects received open-label VOR (6 mg/kg IV every 12 hours on Day 1) followed by 4 mg/kg IV every 12 hours; combination therapy was administered for 2-4 weeks and the investigator could switch to VOR monotherapy after 2 weeks, to complete at least 6 weeks of AF therapy. In this study, the analysis population was defined as those subjects with proven or probably IA confirmed. Through Day 42 all-cause mortality for the VOR monotherapy patients was 27.5% (39/142, 95% CI 20.3, 35.6).

The results published by Maertens et al (2015) [27] were based on a Phase 3, double-blind, global multi-center non-inferiority trial, where patients with suspected invasive mold disease were randomized 1:1 to receive either ISA (equivalent to 200 mg ISA intravenously 3 times a day on Days 1 and 2 then either intravenously or orally once daily) or VOR (6 mg/kg intravenously twice daily on Day 1, 4 mg/kg intravenously twice daily on Day 2, then intravenously 4 mg/kg twice daily or orally 200 mg twice daily from Day 3 onwards). The all-cause mortality rate at Day 42 for ITT patients who received VOR was 20.2% (52/258, 95% CI 15.4, 25.6).

Based on these 3 studies, a random effects meta-analysis gave an overall estimate for all-cause mortality of 23.0% with a 95% asymptotic CI of (16.4, 29.6) [19]. The test for heterogeneity was found to be not significant ($p=0.1443$) based on the Cochran-Mantel-Haenszel (CMH) test.

Table 15 Meta-Analysis (3 studies)

Study	Patient Population	N	All-cause Mortality through Day 42(%) and (95% CI)
307/602	mITT	144	18.8% (27/144) (12.7, 26.1)
Marr et al (2015)	mITT	142	27.5% (39/142) (20.3, 35.6)
Maertens et al (2015)	ITT	258	20.2% (52/258) (15.4, 25.6)
Pooled (raw)		544	21.7% (118/544) (18.3, 25.4)
Pooled (meta-analysis)		544	23.0% (16.4, 29.6)

8.7.1.2 Percentage Effect Size Retained with Selected Margin

The percentage retained by POS in terms of mortality may be better understood as 1 minus the percentage of the effect size that one may be willing to lose given a selected NI margin, i.e. where effect size loss "allowed" is simply the selected NI margin as a percentage of the estimated effect of the active control VOR over placebo (Pbo) with respect to all-cause mortality.

Two different statistical approaches were used and differ as to which estimate of the effect of VOR over Pbo is used in the calculations. In both approaches, the 95% CI lower bound of the Pbo mortality is assumed. We first consider the "point estimate" approach, which takes the point estimate of the VOR mortality and subtracts the assumed Pbo mortality to determine the VOR effect size. The second, more conservative "fixed margin" approach, uses the 95% upper bound of the VOR mortality and subtracts the 95% lower bound of the Pbo mortality to determine the VOR effect size. The second approach is often referred to as the "95-95" method since the NI margin itself represents a 95% lower bound [20]. As a frame of reference, the minimal Pbo mortality that would have to be assumed to preserve at most 50% of the VOR effect is also calculated.

Since there were no Pbo-controlled studies for the treatment of IA, we assumed an all-cause mortality rate for Pbo of 75%. This is based on an internal meta-analysis of historical data from 1952 to 2006 cited in Maertens et al. [27]. That analysis reported the all-cause mortality rate in untreated patients of 84.8% with a 95% CI of (75.1, 94.5). Maertens et al. further indicate that this mortality rate is supported by a rate of 100% in untreated patients reported Denning (1996) [22].

In the first approach, the point estimate of the historical VOR effect is used (23.0% point estimate from the meta-analysis). Thus, the effect size for all-cause mortality of VOR over Pbo is estimated to be 52 percentage points (75% Pbo mortality minus 23% VOR mortality), and thus a NI margin of 10% represents approximately 20% of

this effect size (0.10/0.52). Therefore, ~80% of the effect size of VOR over Pbo is retained with a NI margin of 10%.

A more conservative approach instead uses the upper 95% CI limit for the historical VOR effect, here 29.6%. In this instance, then, the effect size for all-cause mortality of VOR over Pbo is estimated to be 45.4 percentage points (75% Pbo mortality minus 29.6% VOR mortality). A NI margin of 10% would then represent approximately 22% of the VOR effect size over Pbo (0.10/0.454) and ~78% of the effect size is retained.

Under both sets of assumptions, a large majority of the effect size of VOR over Pbo is preserved with a 10% non-inferiority margin. This is summarized in [Table 16](#) below.

Finally, [Table 16](#) also presents the minimal Pbo mortality rate that would have to be assumed in order for a 10% NI margin to preserve exactly 50% of the VOR over Pbo effect size. Using the most conservative estimate for VOR mortality of 29.6%, the minimal Pbo mortality would have to be 49.6%, which is substantially lower than any published mortality rate associated with Pbo found in the literature [25, 26, 19, 27].

Table 16 Percentage (%) of Effect Size Retained with 10% Margin

Method	VOR Mortality	Pbo Mortality	Effect Size (Pbo – VOR)	Percent of Effect Size Preserved with 10% NI Margin (1-0.10/Effect Size)
VOR Point Estimate	23.0%	75%	0.52	80.8%
VOR Upper CI Limit	29.6%	75%	0.454	78.0%
VOR Upper CI Limit, Minimal Pbo Mortality to Preserve 50% of VOR Effect	29.6%	49.6%	0.20	50%

The above calculations present a variety of scenarios and data assumptions supporting a 10% NI margin in this study. All relevant historical data on IA and VOR was reviewed in this assessment. If relevant new data on VOR becomes available in this patient population, the margin justification may be re-assessed.

One strength in establishing 'comparability' of the historical data is the active control treatment in study PN069 is nearly identical to the ones administered in Studies 307/602 studies, i.e., subjects in PN069 start with a VOR IV loading dose of 6 mg/kg IV BID on Day 1 followed by 4 mg/kg VOR IV BID maintenance dose, beginning on Day 2. Subject, if considered clinically stable, can then transition to oral VOR (200 mg BID), for a total of 12 weeks. Although some subjects in PN069, if clinically indicated, will be able to start oral VOR therapy on Day 1 (300 mg BID) followed by 200 mg BID, this difference is believed not to have an impact on the true effect of VOR on all-cause mortality.

The meta-analysis conducted gives credibility to the constancy of the treatment effect of VOR, i.e., a reasonably consistent estimate of the effect was observed. It is apparent that VOR itself is quite active and in the pivotal studies used for registration (Studies 307/602), VOR was not only shown to be non-inferior to AmB, but also superior, as the lower bound of 95% CI of the treatment difference excluded 0.

In summary, two different approaches were used to assess the % of the efficacy retained and included a conservative assessment (95%-95% method) which still resulted in a substantial % of efficacy retained (>50%) under realistic scenarios.

